## **3.2 Analysis Populations**

The following populations will be analyzed:

**Modified Intent-to-treat (mITT) Population**: The primary population for efficacy analyses will be a Modified Intent-to-treat (mITT) Population defined as all subjects who receive at least 1 dose of study medication. The mITT Population will be used for tables of demography, baseline characteristics, and efficacy.

**Safety Population**: The Safety Population is defined as all subjects who receive at least 1 dose of study medication. In this study, the Safety Population is equivalent to the mITT Population.

**Subpopulation:** Two protocol defined subpopulations based on EGFR biomarkers EGFR at baseline are as follows

Subpopulation	Description
А	Patients with an assumed beneficial mutation (EGFR gene amplified glioblastoma)
В	Patients with an assumed beneficial mutation (EGFRvIII pos glioblastoma)

These two biomarkers are the targets for tesevatinib treatment.

## 3.3 Subject Disposition and Evaluability

Subjects who failed screening (i.e., subjects who signed the informed consent were screened but never started the study treatment, and their basic demographics and any AE after signing the informed consent may have been collected in the CRF) will be excluded from any populations defined in Section 3.2. Therefore, these subjects will be excluded from any summary tables or listings.

The number of subjects discontinuing from the study and the primary reason for discontinuation will be summarized.

## **3.4 Protocol Deviations**

All protocol deviations will be identified and classified as major or minor before clinical database lock and will be presented in a listing.

**Major Deviation**: Protocol deviation that may impact the accuracy, and/or reliability of the study data or that may impact subject rights, safety or well-being.

**Minor Deviation**: Protocol deviation that does not impact the accuracy, and/or reliability of the study data or subject rights, safety or well-being.

## 3.5 Demographics and Baseline Characteristics

## 3.5.1 Demographics

Subject demographics and baseline characteristics will be summarized for the mITT Population. Descriptive statistics will be provided for age, height, and weight.

## 3.5.2 Medical History

Medical history will be summarized by primary System Organ Class (SOC) and Preferred Term (PT). Medical history will be coded using Medical Dictionary for Regulatory Activities (MedDRA) Version 20.1 (or higher) terminology.

## 3.5.3 Baseline GBM Disease Characteristics

- Months since first GBM diagnosis
- Months since recurrent GBM diagnosis
- Tumor Measurement
- Diagnosis of Prior Low Grade Astrocytoma

## **3.5.4 Other Baseline Characteristics**

Other baseline values including Karnofsky Performance Scale (Appendix E; Karnofsky et al., 1949) and childbearing potential will also be summarized.

## 3.6 Prior and Concomitant Medications

## 3.6.1 Medications and procedures for GBM

- Prior radiotherapy
- Prior systemic therapy
- Corticosteroid use at baseline

## **3.6.2** Other Prior and Concomitant Medications

Concomitant medications will be coded using the World Health Organization Drug Dictionary. Prior medications are defined as those medications that began and stopped before the start of study treatment. Concomitant medications are defined as medications taken after the start of study treatment and during the study period, including those began before but ongoing at the start of study treatment. If a medication start date is partially or fully missing and it is unclear as to whether the medication is prior or concomitant, it will be assumed that the medication is concomitant.

Number and percentage of incidence of prior and CM will be summarized according to Anatomical Therapeutic Class (ATC) and preferred drug name.

## 3.7 Treatment Compliance and Exposure

The amount of tesevatinib administered by visit and overall (total dose) will be tabulated and presented by patient in data listings. The distribution of the number of cycles achieved per patient will also be summarized. In addition, delays and all other alterations in tesevatinib administration will be presented

## **3.8 Primary Endpoint Analysis**

## 3.8.1 Progression-Free Survival Rate at 6 Month (PFS-6)

Proportion of patients who are alive and not progressed at 6 months (24 weeks) will be analyzed with method as described in3.1.4.2. This analysis is based on mITT population. Patients whose survival or response status at 6 months (24 weeks) are unknown are not considered alive or progression free. Response Assessment in Neuro-Oncology (RANO) criteria are used to determine specific criteria for treatment response (Appendix 2 of the protocol.) in all endpoint analysis in this study.

#### **3.8.2** Secondary Endpoint Analyses

#### 3.8.2.1 PFS-6 in Subpopulations A and B, as well as combination of And B

Progression-Free Survival rate at 6 months will be analyzed with method as described in 3.1.3.2 respectively in subpopulations A and B, and the combination of A and B.

#### 3.8.2.2 OS-9 in Subpopulations A and B, as well as in mITT

Survival rate at 9 months will be analyzed with method as described in 3.1.4.2 respectively in subpopulations A and B, and in mITT population.

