#### 13.4.6.2. Secondary efficacy endpoints

The following subgroup PFS-6 endpoints:

- Investigator-assessed PFS-6 in the subgroup of patients with EGFRvIIIpos glioblastoma
- Investigator-assessed PFS-6 in the subgroup of patients with EGFR gene amplified glioblastoma

are evaluated using the same methodology as for the primary endpoint. The analysis is performed by including a subgroup factor as fixed effect in the model used to analyze the primary endpoint. PFS-6 with 95% confidence intervals are estimated for each subgroup as well as for the residual population.

Comparison of the efficacy between the subgroups and the residual group is performed by estimating the hazard ratio (HR) with 2-sided 95% and 80% confidence intervals and the p-value for the null hypothesis: HR=1.

Furthermore, Kaplan-Meier methodology will be used to estimate median PFS with 95% CI using Greenwood's formula and the Kaplan-Meier curves will be constructed to provide a visual description of the PFS for the subgroups over time.

Descriptive statistics overall and for each parameter in the disease progression assessment are presented for the entire assessment period as well as for 3, 6 and 9-month time points by subgroup.

The secondary endpoint:

• OS rate at 9 months (OS-9) and OS overall, in all patients and in those with EGFRvIIIpos and EGFR gene amplified glioblastoma

where OS is defined as the time between date of first dose of study drug and the date of death due to any cause. OS-9 is defined as the percentage of patients who are alive at 9 months.

Kadmon Corporation	Page 89 of 113	03 Apr 2019
	Confidential and	
	Proprietary	

Patients who are not reported as having died at the time of analysis will be censored at the date when they were last known to be alive; if no post-baseline data are available, OS will be censored at the date of first study drug. The analysis methods will be the same as for the PFS.

The secondary endpoints:

• ORR per RANO criteria, and DOR in all patients and in those with EGFRvIIIpos and EGFR gene amplified tumors

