## 3.1.2 Changes from protocol

Changes from protocol in statistical methods are made in both primary and secondary analyses wherever necessary.

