#### 3.1.4.2 Binary Endpoint and Other Categorical Variables

For endpoints with two possible outcomes such as alive/otherwise or response/otherwise within specific periods, the 95% confidence interval will be calculated with Clopper-Pearson method for survival rates or response rates. For

other categorical variables, the counts and percent of each category within a parameter will be calculated for observed data only. The denominator for all percentages, unless otherwise specified, will be the number of subjects in the cohort or in the specified analysis population.

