## 3.1.7 Handling of Incomplete or Missing Data

Missing data will not be imputed in general and will be reported as missing in all listings. For categorical variables, patients with missing data are not included in calculations of percentages unless otherwise specified.

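### OS-9 is planned as an uncensored proportion although OS is censored in both documents, and no rule covers a patient whose 9-month status is unknown

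*SAP*

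**What the plan says.** **Method for OS-9.** SAP 3.8.2.2: "Survival rate at 9 months will be analyzed with method as described in 3.1.4.2", in Subpopulations A and B and in mITT. SAP 3.1.4.2 opens "For endpoints with two possible outcomes such as alive/otherwise or response/otherwise within specific periods" and continues that "the 95% confidence interval will be calculated with Clopper-Pearson method for survival rates or response rates". On the denominator it adds: "The denominator for all percentages, unless otherwise specified, will be the number of subjects in the cohort or in the specified analysis population".

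**Treatment of OS.** Protocol 13.4.6.2 gives the definition "OS-9 is defined as the percentage of patients who are alive at 9 months", censors patients not reported dead at the date last known alive, and applies the PFS analysis methods. For a landmark rate, protocol 13.4.6.1 uses a shared gamma-frailty Cox model. SAP 3.1.4.4 censors OS at last known alive or study cut-off, whichever is earlier, and 3.8.2.4 plans Kaplan-Meier OS in the same three populations.

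**Unknown status.** The one explicit rule is in SAP 3.8.1 and is written for the 6-month endpoint: "Patients whose survival or response status at 6 months (24 weeks) are unknown are not considered alive or progression free". The general rule in SAP 3.1.7 is: "For categorical variables, patients with missing data are not included in calculations of percentages unless otherwise specified".

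**Changes from protocol.** SAP 3.1.2 says only: "Changes from protocol in statistical methods are made in both primary and secondary analyses wherever necessary".

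**Follow-up.** Protocol 13.4.1 sets statistical completion at six months after the last patient starts treatment. The synopsis says long-term follow-up is not required as of Amendment 4. The synopsis (study design), 7.1 and 12.2.14 still describe survival contact every 8 weeks. The OS cut-off in SAP 3.1.4.4 carries no date.

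**The concern.** The SAP treats the same survival data in two ways: censored for the OS curve, uncensored for OS-9. The two agree when every patient's 9-month status is known. When it is not, the proportion needs a scoring rule, and the SAP has none for 9 months. Two programmers could report different OS-9 values from one data set, and neither value need match the Kaplan-Meier curve at 9 months in the same report.

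Unknown status is foreseeable. A cut six months after the last start falls short of a 9-month landmark for late enrollees, and long-term follow-up stopped being mandatory part-way through the trial.

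At stake is a secondary efficacy estimate in all patients and in both EGFR subpopulations. If a censored patient who was alive is scored as not alive, the result describes the share known to be alive at 9 months, which is lower than 9-month survival.

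**Working it through.** The documents give no OS-9 target, power or dropout rate, so there is no planned figure to reproduce. The check covers the possible readings, the effect of one patient, and how the estimators differ.

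**1. Readings of the SAP**

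- Not alive: 3.1.4.2 divides patients into alive and otherwise, over the whole analysis population. An unknown patient falls in the second group. The 6-month rule in 3.8.1 is a precedent but does not extend to 9 months.
- Dropped: 3.1.7 removes missing values from percentages.
- Both the 3.1.4.2 denominator rule and the 3.1.7 rule yield to anything specified elsewhere, so neither clearly overrides the other. Not alive is the more natural reading, but it is an inference.

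**2. Effect of one patient**

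Inputs: n = 40 (SAP 2.2); assumed shares 57% in A and 27% in B (protocol Table 7), so 0.57 × 40 = 22.8, about 23, and 0.27 × 40 = 10.8, about 11.

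Scoring one living patient as not alive lowers OS-9 by 1/n:

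- mITT: 1/40 = 2.5 points
- A: 1/23 = 4.3 points
- B: 1/11 = 9.1 points

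**3. Worked example (hypothetical counts)**

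Of 40 patients, 16 are known alive at 9 months, 20 are dead (deaths evenly spaced from 0.4 to 8.8 months) and 4 are censored at 6.2, 6.9, 7.6 and 8.3 months.

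- Not alive: 16/40 = 40.0% (Clopper-Pearson 24.9 to 56.7)
- Dropped: 16/36 = 44.4% (27.9 to 61.9)
- Kaplan-Meier: 26/40 × 24/25 × 21/23 × 19/20 × 16/18 = 48.1% (log-log 31.6 to 62.9)
- All unknown alive: 20/40 = 50.0% (33.8 to 66.2)

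With complete follow-up and 20 of 40 alive, Kaplan-Meier and the proportion are both 50.0%.

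**4. Administrative censoring (assumptions not in the documents)**

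Assume exponential OS with a 9-month median, consistent with the protocol's background figure of under 10 months. True OS-9 is then 0.50 and λ = ln 2 / 9 = 0.0770 per month. Assume uniform accrual over 12 months and a data cut exactly 6 months after the last start.

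- Share with at least 9 months of potential follow-up: 1 − 3/12 = 0.75
- Known alive, which is the not-alive estimate: 0.50 × 0.75 = 0.375
- Unknown: (e^(−6λ) − e^(−9λ)) / (12λ) = (0.630 − 0.500) / 0.924 = 0.141
- Dropped: 0.375 / (1 − 0.141) = 0.436
- Kaplan-Meier: 0.50, because this censoring is independent of survival

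A later cut removes the effect.

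**5. Informative loss (assumptions not in the documents)**

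The true OS-9 is again 0.50.

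| Loss mechanism | Share affected | Not alive | Dropped | Kaplan-Meier |
|---|---|---|---|---|
| Follow-up ends 1 month after progression | 25% | 0.39 | 0.49 | 0.52 |
| Same | 50% | 0.28 | 0.46 | 0.54 |
| Contact lost 1 month before death | 10% | 0.50 | 0.53 | 0.53 to 0.54 |
| Same | 25% | 0.49 | 0.57 | 0.59 |
| Same | 50% | 0.48 | 0.66 | 0.70 |

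The first two rows use Weibull PFS with median 4.5 months and PFS-6 of 25%, and exponential post-progression survival with mean 5.81 months. The last three use the exponential OS of step 4. Kaplan-Meier is too high in every row. It is nearer the truth than the not-alive proportion in the first two rows and further away in the last three. The dropping reading errs in either direction.

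**The case against.** The strongest case for the plan has four parts.

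*The proportion matches the definition.* The protocol defines OS-9 as a percentage alive, and the SAP handles OS-9 and PFS-6 alike, much as the protocol does. That stands as far as it goes. But the protocol's shared method accommodates censoring and the SAP's does not, and the SAP does not name the switch. A Kaplan-Meier landmark also departs from the protocol's Cox model, so it too must be listed.

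*Unknown status may be rare.* Statistical completion is not the OS data cut. The SAP is dated 23 June 2020, more than 14 months after Amendment 4 (3 April 2019), so the actual cut may be late, and the amendment cannot affect patients already past 9 months by then. This stands, and it is why the size may be zero. A reader might also infer from the 30-day follow-up in SAP 2.2 that survival contact stopped then. The documents do not support that: the protocol has a similar 30-day sentence in 9.1.2 alongside 8-weekly survival contact, and the SAP sentence resembles the adverse-event window.

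*Kaplan-Meier is not always better.* This stands. If contact is lost shortly before death, the planned proportion is nearly right and Kaplan-Meier is inflated, the flattering direction in a single-arm trial.

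*The consequence is small.* OS curves are already planned, and OS-9 has no power, target or decision rule. This stands and sets the weight of the point.

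**Conclusion.** The inconsistency and the missing rule are certain from the text. OS-9 is analysed without censoring, OS is censored in both documents, SAP 3.1.2 does not name the change, and unknown 9-month status has no stated handling.

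The bias is conditional. It needs the not-alive reading and at least one patient of unknown status who was alive at 9 months. The understatement is then up to 2.5 points per such patient in mITT, and about 4.3 in A and 9.1 in B if the Table 7 shares hold. The number of such patients cannot be derived.

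Two stronger conclusions are tempting and unsupported. One is that OS-9 will be biased low: with complete 9-month status there is no bias, and under the dropping reading the direction depends on why patients were lost. The other is that Kaplan-Meier is closer to the truth whatever the reason for loss: the last three rows of the table contradict it. The simulated values rest on assumed accrual, survival and loss patterns. They show direction only and do not raise the weight of the point.

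The endpoint is secondary and unpowered, and PFS-6 is unaffected. This is a minor point that merits a wording change.

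**What to change.** 1. In SAP 3.8.2.2, estimate OS-9 as the Kaplan-Meier survival probability at 9 months with a Greenwood (log-log) 95% confidence interval, from the OS analysis in 3.1.4.4, in mITT and in Subpopulations A and B.
2. Always report with it the number censored before 9 months and two bounds: all unknown dead (known alive over the population, which is the proportion now planned on its natural reading) and all unknown alive.
3. List the change in SAP 3.1.2 as a departure from protocol 13.4.6.2, with the reason.
4. State the OS cut-off date in SAP 3.1.4.4.
5. Reconcile the survival follow-up passages: the protocol synopsis (8-weekly contact against long-term follow-up not required as of Amendment 4), 7.1, 12.2.14 and SAP 2.2.

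If the proportion is kept, the minimum is to state the unknown-status rule for 9 months and report the number unknown with both bounds.

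The cost is SAP wording and a few table cells. The Kaplan-Meier analysis is already planned, the current proportion survives as the lower bound, and no new data are needed. The downside is that Kaplan-Meier is biased upward if patients are lost after progression or shortly before death, and can then be further from the truth than the proportion. It should not be shown without the bounds.

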#### 3.8.2.3 PFS in Subpopulations A and B, as well as in mITT

PFS will be analyzed with method as described in 3.1.4.3 respectively in subpopulations A and B, and in mITT population.

#### 3.8.2.4 OS in Subpopulations A and B, as well as in mITT

OS will be analyzed with method as described in 3.1.4.4 respectively in subpopulations A and B, and in mITT population.

## 3.8.2.5 Objective Response Rate (ORR) and DOR per RANO

ORR including CR or PR per RANO criteria will be analyzed with method as described in 3.1.4.2 respectively in subpopulations A and B, and in mITT population. This analysis will be performed in subpopulations A and B, and in mITT population.

For responders in above analyses, corresponding Duration of response is calculated as the time from first documented evidence of CR or PR (whichever status is recorded first) until the first documented sign of disease progression or death due to any cause (whichever is the first). DOR will be summarized

It is defined for subjects with a confirmed CR or a confirmed PR. For subjects in the subset of responders who do not progress or die, duration of response will be analyzed with method as described in 3.1.4.3.

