- 8. First recurrence after concurrent or adjuvant chemoradiotherapy. Imaging confirmation of first tumor progression or regrowth as defined by the RANO criteria. A minimum of 12 weeks must have elapsed from the completion of radiotherapy to study entry to minimize the potential for MRI changes related to radiation necrosis that might be misdiagnosed as progression of disease, unless there is a new lesion outside the radiation field or unequivocal evidence of viable tumor on histopathological sampling.
- 9. Prior treatment with TMZ for low grade glioma or glioblastoma.
- 10. No more than one prior line of systemic treatment for glioblastoma. Concurrent and adjuvant TMZ-based chemotherapy, including the combination of TMZ with an investigational agent, is considered one line of therapy.
- 11. Prior therapy with gamma knife or other focal high-dose radiotherapy is allowed, but the patient must have subsequent histologic documentation of recurrence, unless the recurrence is a new lesion outside the irradiated field.
- 12. Recovery from the toxic effects of prior therapy, with a minimum time of:
  - a.  $\geq 28$  days elapsed from the administration of any investigational agent
  - b.  $\geq 28$  days elapsed from the administration of any prior cytotoxic agents, except  $\geq 14$  days from vincristine,  $\geq 21$  days from procarbazine, and  $\geq 42$  days from nitrosureas
  - c.  $\geq$  14 days elapsed from administration of any non-cytotoxic agent (e.g., interferon, tamoxifen, thalidomide, cis-retinoic acid)
- 13. Patients who have undergone recent surgery for recurrent or progressive tumor are eligible provided that:
  - a. Surgery must have confirmed the recurrence
  - b. There must be residual disease measurable per RANO criteria e.g. 1 cm x 1 cm
  - c. A minimum of 28 days must have elapsed from the day of surgery to first dose of the study drug. For core or needle biopsy, a minimum of 7 days must have elapsed prior to study entry
- 14. Availability of formalin-fixed paraffin-embedded tumor tissue diagnostic of glioblastoma.

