where ORR is defined as a CR or PR. Patients without a post-baseline disease assessment will be considered as non-responders. The analysis population for ORR will be all enrolled patients with measurable disease at baseline. An estimate of ORR and its 95% CI will be calculated using the Blyth-Still-Casella method for each treatment arm. CIs for the difference in ORRs between the subgroups will be determined using the normal approximation to the binomial distribution. In addition, ORR is analyzed with a generalized logistic regression analysis. Subgroup is included as fixed effect, KPS as a covariate and study center as random effect. The adjusted odds ratio for being a responder is estimated and the two-sided 95% confidence interval presented.

DOR is defined as the time from the initial response to disease progression or death among patients who have experienced a CR or PR during study. Patients who have not progressed or died at the time of analysis will be censored at the last disease assessment date. DOR will be estimated using Kaplan- Meier methodology. Comparisons between subgroups through use of the unstratified log-rank test will be made for descriptive purposes only.

- To evaluate the efficacy of tesevatinib as measured by PFS-6, OS-9, RANO ORR and DOR in the subgroups:
  - EGFRvIIIpos vs EGFRvIIIneg
  - EGFR amplificationpos vs EGFR amplificationneg

The statistics for these subgroup comparisons are described at each of the endpoints.

In addition, statistics for the change and percent change from baseline tumor measurements will be presented. These analyses will be done after each two cycles of therapy. Summary statistics will be produced for PFS and OS. The percentage of patients without disease progression after 3 and 6 months of dosing will also be presented separately by local (investigator) and potentially by central radiography results. Sites will provide copies of all MRI image sets for central retention in case central radiology review is required.

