# APPENDIX 2. RANO CRITERIA

Response	Criteria
Complete response (CR)	
 
Requires all of the following:
 
Complete disappearance of all enhancing measurable and nonmeasurable disease sustained for at least 4 weeks.
 

Bastial	
 
No new lesions
 
Stable or improved non-enhancing (T2/FLAIR) lesions
 
Patients must be off corticosteroids (or on physiological replacement doses only)
 
Clinical status is stable or improved
 

response (PR)	
 
≥ 50% decrease compared with baseline in the sum of products of perpendicular diameters of all measurable enhancing lesions sustained for at least 4 weeks
 
No progression of nonmeasurable T1enhancing disease
 
No new lesions
 
Stable or improved non-enhancing (T2/FLAIR) lesions on the same or lower dose of corticosteroids compared to baseline
 
Clinical status is stable or improved
 
Note: Patients with nonmeasurable disease only cannot have a partial response; the best response possible is stable disease
 

Stable disease (SD)	
 
Requires all of the following:
 
Patient does not qualify for complete response, partial response, or progression
 
Stable non-enhancing (T2/FLAIR) lesions on same or lower dose of corticosteroids compared to baseline
 
Clinical status is stable or improved
 
Note: In the event that the corticosteroid dose was increased for new symptoms and signs without confirmation of disease progression on neuroimaging, and subsequent follow-up imaging shows that this increase in corticosteroids was required because of disease progression, the last scan considered to show stable disease will be the scan obtained when the corticosteroid dose was equivalent to the baseline dose.
 

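### The SAP drops the protocol's measurable-disease restriction on ORR without naming the change, so any dosed patient with only nonmeasurable disease would count as a non-responder

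*SAP*

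**What the plan says.** The two documents define the ORR population differently.

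- **Protocol 13.4.6.2** has a rule for this endpoint alone: "The analysis population for ORR will be all enrolled patients with measurable disease at baseline". It adds that patients with no disease assessment after baseline count as non-responders.
- **SAP 3.8.2.5** analyses ORR by the method of SAP 3.1.4.2 and states: "This analysis will be performed in subpopulations A and B, and in mITT population". It has no restriction on measurability.
- **SAP 3.2** gives mITT as "defined as all subjects who receive at least 1 dose of study medication".
- **SAP 3.1.4.2** sets the denominator: "The denominator for all percentages, unless otherwise specified, will be the number of subjects in the cohort or in the specified analysis population". Nothing else is specified for ORR.
- **SAP 3.1.2** says in general terms that methods were changed in the primary and secondary analyses. It does not mention the ORR population or give a reason.

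Three other places in the protocol determine whether the difference matters.

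- **Section 8.2, criterion 13b** is the only eligibility text that asks for measurable disease: "There must be residual disease measurable per RANO criteria e.g. 1 cm x 1 cm". It sits under a condition of limited scope: "Patients who have undergone recent surgery for recurrent or progressive tumor are eligible provided that". Criterion 8, which covers everyone, asks for imaging-confirmed first progression or regrowth by RANO.
- **Appendix 2** states: "Patients with nonmeasurable disease only cannot have a partial response; the best response possible is stable disease". It also lists clear progression of nonmeasurable disease among the routes to a RANO progression.
- **Section 13.4.1 and the synopsis** say in general terms that the primary and secondary efficacy analyses cover everyone in the study.

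**The concern.** A patient with only nonmeasurable disease cannot be a responder under the trial's own criteria. In the denominator, such a patient lowers ORR whatever the drug does. The protocol's restriction is consistent with Appendix 2. The SAP's population is not, and the reader is not told that it changed.

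What is at stake is how a secondary endpoint is read. ORR would depend partly on how many nonmeasurable-only patients happened to enter. A reader who assumes the protocol's definition would compare it with the wrong quantity. The same denominator question arises in Subpopulations A and B, which are small enough for a few patients to move the rate by several points.

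**Working it through.** **1. Can the two populations differ?** Criterion 13b binds only patients with recent surgery for recurrence. Every other patient qualifies through criterion 8, and by Appendix 2 a RANO progression can rest on nonmeasurable disease. A nonmeasurable-only patient can therefore be eligible and dosed. The documents do not say that any such patient was enrolled.

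**2. Formula.** Let n be the number dosed, m the number of those without measurable disease, and x the number of responders. By Appendix 2 all x responders lie among the n − m. For the arithmetic, enrolled and dosed are taken to be the same patients.

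- Protocol rate = x / (n − m)
- SAP rate = x / n = protocol rate × (1 − m/n)

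**3. Inputs.** n = 40 is the planned size (protocol 13.2). The documents give no target, null rate or power for ORR, so there is no stated figure to reproduce. They do not give m or x either. Here x = 4 and m = 0, 4, 8 or 12 are assumptions. Both columns use the SAP's Clopper-Pearson interval, so that only the denominator changes. (Protocol 13.4.6.2 names Blyth-Still-Casella.)

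| Assumed m | 1 − m/n | SAP rate (95% CI) | Protocol rate (95% CI) | Difference, points |
|---|---|---|---|---|
| 0 | 1.0 | 4/40 = 10.0% (2.8 to 23.7) | 4/40 = 10.0% (2.8 to 23.7) | 0.0 |
| 4 | 0.9 | 4/40 = 10.0% (2.8 to 23.7) | 4/36 = 11.1% (3.1 to 26.1) | 1.1 |
| 8 | 0.8 | 4/40 = 10.0% (2.8 to 23.7) | 4/32 = 12.5% (3.5 to 29.0) | 2.5 |
| 12 | 0.7 | 4/40 = 10.0% (2.8 to 23.7) | 4/28 = 14.3% (4.0 to 32.7) | 4.3 |

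**4. Subpopulations.** Protocol Table 7 assumes 57% in A and 27% in B: 0.57 × 40 = 22.8, about 23 patients, and 0.27 × 40 = 10.8, about 11. The counts of responders and of nonmeasurable patients below are again assumptions.

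- A, with 4 responders and 5 nonmeasurable: SAP 4/23 = 17.4%, protocol 4/18 = 22.2%.
- B, with 2 responders and 2 nonmeasurable: SAP 2/11 = 18.2%, protocol 2/9 = 22.2%.

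**The case against.** The strongest reply is that the SAP follows other protocol text. Protocol 13.4.1 and the synopsis put all patients into the secondary efficacy analyses and treat everyone who takes a dose as evaluable for efficacy. The SAP's mITT fits that. It would then be wrong to infer that the SAP simply contradicts the protocol, because part of the conflict lies inside the protocol. This stands as far as it goes. But the ORR sentence in 13.4.6.2 is the more specific one and would have no purpose if the general sentence overrode it. Either way, the passages need reconciling.

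A second reply is that response among all treated patients is a legitimate, conservative quantity. That is also true, and it supports keeping the all-mITT rate as a labelled line. It does not justify replacing the protocol's definition without naming the change.

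A third is that the effect is small or nil. It is zero if no nonmeasurable-only patient is dosed, and the assumed shifts of 1.1 to 4.3 points are small beside an interval of 2.8% to 23.7%. SAP 3.1.3 claims no power for secondary endpoints, and the futility rule in protocol 13.3 uses PFS-6, not ORR. All of this stands and limits the weight of the point.

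**Conclusion.** The point holds as an undeclared change of the ORR population. Measured against the protocol's definition, the SAP's ORR is lower by the factor (1 − m/n). There is no effect at m = 0. With an assumed 4 responders among 40, the SAP's 10.0% stands against 11.1%, 12.5% or 14.3% for assumed m of 4, 8 or 12. Neither m nor the responder count comes from the documents.

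Two stronger readings go beyond the text.

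- A reader might infer that ORR is in fact biased downward. The documents show only that eligibility permits such patients, not that any were dosed.
- A reader might infer that the comparison of EGFR-positive with EGFR-negative patients is distorted. That needs nonmeasurable disease to be unevenly spread between the groups, and the documents say nothing on this. SAP 3.8.2.6 lists the two comparisons without a method or population, so its denominator is itself an inference.

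The primary PFS-6 analysis is not affected. The sponsor should make the change, but it is not critical to the trial's main conclusion.

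**What to change.** In SAP 3.8.2.5, and for the ORR comparison in 3.8.2.6:

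- Set the main ORR denominator to patients with measurable disease at baseline, overall and within each EGFR group.
- Keep patients with measurable disease but no assessment after baseline as non-responders. Protocol 13.4.6.2 requires this, and SAP 3.8.2.5 does not repeat it.
- State whether the set is drawn from enrolled patients, as the protocol has it, or from dosed patients, as mITT has it. Record that choice in SAP 3.1.2.
- State the definition of measurable disease behind the flag, since criterion 13b gives only an example size.
- Report the number without measurable disease, overall and by EGFR group.
- Keep the all-mITT rate as a labelled supportive line.

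In the protocol, reconcile the general all-patients sentence in 13.4.1 and the synopsis with the ORR rule in 13.4.6.2.

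The cost is some wording and one population flag. Baseline tumour measurement is already collected and listed in SAP 3.5.3. The downside is a slightly smaller denominator and a slightly wider interval: in the example with m = 4, 3.1% to 26.1% instead of 2.8% to 23.7%.
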